## APPENDIX

---

### **Operationalization of post-infective fatigue syndrome (PIFS) caseness (modified Fukuda definition) at 6 months**

---

#### 1. The Fukuda definition, main criteria for PIFS (patients must adhere to all)

a) CFQ (Chalder Fatigue Questionnaire), total sum score at 6 months (dichotomous scoring 0-0-1-1 of single items)	≥ 4	Definition of fatigue caseness applied in several publications.
b) CFQ total sum score at baseline	≥ 4	Ensures persistence of fatigue from the acute infectious event. Corresponds to the “fatigue severely affects daily activities” criterion, and to a chronic disease of “moderate” severity.
c) SF-36; total score		
a) PEM (post-exertional malaise) frequency	≥ 2 for at least 1 of 5 items	From the DePaul symptom questionnaire. Corresponds to the “fatigue not alleviated by rest” criterion

#### 2. The Fukuda definition, additional criteria for PIFS (criterion h) and i) are merged; patients must then adhere to at least 4 of 8)

a) “... experienced fatigue the day after an exertion”	≥ 3	Single item (5-point Likert scale, 3 indicates 1-2 times a week) from questionnaire
b) “... experienced headache”	≥ 3	Single item (5-point Likert scale, 3 indicates 1-2 times a week) from questionnaire
c) “... experienced sore throat”	≥ 3	Single item (5-point Likert scale, 3 indicates 1-2 times a week) from questionnaire
d) “... experienced tender cervical lymphatic nodes”	≥ 3	Single item (5-point Likert scale, 3 indicates 1-2 times a week) from questionnaire
e) “... experienced muscle pain”	≥ 3	Single item (5-point Likert scale, 3 indicates 1-2 times a week) from questionnaire
f) “... experienced multi-joint pain”	≥ 3	Single item (5-point Likert scale, 3 indicates 1-2 times a week) from questionnaire
g) “... experienced unrefreshing sleep”	≥ 3	Single item (5-point Likert scale, 3 indicates 1-2 times a week) from questionnaire
h) “... experienced concentration problems”	≥ 3	Single item (5-point Likert scale, 3 indicates 1-2 times a week) from questionnaire
i) “... experienced memory problems”	≥ 3	Single item (5-point Likert scale, 3 indicates 1-2 times a week) from questionnaire

#### 3. Exclusion of other states that may explain fatigue (screening followed by individual evaluation)

##### 3.1. SCREENING (INDIVIDUALS MUST ADHERE TO ALL IN ORDER TO REMAIN AS CASES; NON-ADHERENTS ARE SUBJECTED TO INDIVIDUAL EVALUATION, CF POINT 3.2)

a) HADS-A (Hospital Anxiety and Depression Scale, anxiety subscore)	≤ 10	Screening for anxiety. Score of 8-10 corresponds to “possible” anxiety caseness, 11-15 corresponds to “probable” anxiety caseness. A cut-off of 10 is reported to
---	------	---

b) HADS-D (Hospital Anxiety and Depression Scale, depression subscore)	≤ 10	be optimal in a previous study of screening tools for psychiatric comorbidities in CFS/ME. Score of 8-10 corresponds to “possible” depression caseness, 11-15 corresponds to “probable” depression caseness A cut-off of 10 is reported to be optimal in a previous study of screening tools for psychiatric comorbidities in CFS/ME
c) KSQ (Karolinska Sleep Questionnaire, total score)	≥ 2	Screening for primary sleep disorder
d) Other disorder/use of medications that may explain fatigue	No one	As reported in questionnaire, eg. psychiatric, cardiac, pulmonary, or rheumatic disease.
e) Substance abuse that may explain fatigue	No one	As reported in questionnaire

3.2. INDIVIDUAL EVALUATION OF POTENTIAL EXCLUSIONS (INDIVIDUALS **EXCLUDED** AS CASES MUST ADHERE TO ALL)\*

a) Is it likely that the disorder/aberration is causally related to persistent fatigue? Yes

\*Individual evaluation is performed independently by two researchers, using all available information such as recorded data in the present project as well as patients' hospital and GP records. If disagreement about classification, cases are discussed with the principal investigator of the project until consensus is reached. A sensitivity analysis will be carried out excluding all cases with uncertain classification.

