## 1. DESIGN

### Design overview

The proposed study is a 2-arm pragmatic randomised controlled trial (RCT) in which 310 patients who suffer from post-Covid syndrome are randomised to either a short-time outpatient-based rehabilitation program (the intervention) or care as usual in a 1:1 ratio (Fig. 1). Assessments will take place immediately before randomisation (T0), after intervention or care as usual (T1), and 12 months after T0 (T2). Of note, the timing of T1 will vary in the intervention group, due to the individualized therapy approach (cf. below); T1 in the non-intervention group will be matched accordingly. Patients will be recruited from General Practitioners (GP's) as well as social media and self-referral to the involved institutions, and included based upon the criteria listed in Table 1.

---

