### Effect monitoring

Effect monitoring is primarily based on patient reported outcome measures (PROM), applying a web-based questionnaire composed of several validated instruments. The questionnaire will be distributed to the participants at T0, T1 and T2. It will chart clinical symptoms as well as background, psychological and social variables, and will be used for subgrouping according to case definitions of post-COVID-19 syndrome and post-infective fatigue syndrome. The SF-36 subscale Physical Functioning (SF-36-PFS) score at T1 will serve as the **primary endpoint**.

Secondary endpoints include score of PROM inventories at T1 and T2, such as:

- *The Chalder Fatigue Questionnaire (CFQ)* charts subjective experience of physical and mental fatigue. In this study, the CFQ total linear score (i.e. the sum across all 11 items, each item scored on a zero to three Likert scale) will be applied. Furthermore, fatigue

caseness is defined as a CFQ total dichotomous score of 4 or higher (each item scored 0-0-1-1).

- *The Hospital Anxiety and Depression Scale (HADS)* is a validated questionnaire for charting symptoms of depression and anxiety. It consists of 14 items rated zero to three on Likert scales, allowing computation of sub-scores for depression and anxiety symptoms. In the present study, these sub-scores as well as total sum score will be applied.
- *Adverse effects*: A self-invented questionnaire will address possible adverse effect related to the intervention.

Cf. protocol with appendix for at detailed overview of inventories. In addition, employment status, usage of social security-systems (i.e. short and long-term sick leave), and usage of health care services (i.e. the number of GP and specialist contacts, hospitalisations, medications, usage of rehabilitation services, etc.) will be charted through register linkage (cf. below) as well as questionnaires to the study participants.

Also, recovery from post-infective fatigue syndrome will serve as an endpoint. The appendix of the present statistical analysis plan provides an operationalization of post-infective fatigue syndrome according to the Fukuda-definition within the context of the present study.

[figure not shown]

Figure 1. Overview of study design

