### 3. ANALYSIS SETS

#### **Full analysis set**

The ‘full analysis set’ is defined as all patients who were included and randomised. This ‘full analysis set’ will be used for intention-to-treat analyses of efficacy. Missing values will be imputed based on the principle of multiple imputation, given a “missing-at-random”-pattern.

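### The SAP's only stated sensitivity analysis excludes patients of uncertain PIFS classification; applied to recovery at T1 or T2, it would select randomised patients on outcome, with no fixed direction of effect

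*SAP*

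**What the plan says.** - **Endpoint.** SAP section 1 (Effect monitoring) states that "recovery from post-infective fatigue syndrome will serve as an endpoint" and that the appendix "provides an operationalization of post-infective fatigue syndrome according to the Fukuda-definition within the context of the present study". It gives no visit, denominator or definition of recovery.
- **Time point.** The appendix heading reads "caseness (modified Fukuda definition) at 6 months". Its first main criterion takes the Chalder score at 6 months, and its second takes it at baseline. Six months is not one of the trial's visits: T0 is just before randomisation, T1 follows treatment or usual care, and T2 is 12 months after T0.
- **Case rule.** A case must meet all main criteria (appendix 1) and at least 4 of 8 additional symptoms (appendix 2). Appendix 3.1 then screens on anxiety, depression, sleep, other disorders or medication, and substance abuse: "INDIVIDUALS MUST ADHERE TO ALL IN ORDER TO REMAIN AS CASES; NON-ADHERENTS ARE SUBJECTED TO INDIVIDUAL EVALUATION". Appendix 3.2 asks whether the disorder is a likely cause of the persistent fatigue; a yes removes case status.
- **Disputes.** Two researchers rate independently. If they disagree, "cases are discussed with the principal investigator of the project until consensus is reached".
- **Sensitivity analysis.** "A sensitivity analysis will be carried out excluding all cases with uncertain classification". Uncertain is not defined.
- **Other use of the definition.** SAP section 4 (Subgroup analyses) uses PIFS caseness at T0 as the subgrouping variable.
- **Analysis population.** The full analysis set, used for intention-to-treat efficacy analyses, "is defined as all patients who were included and randomised".

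**The concern.** A sensitivity analysis for a judged classification should show whether the conclusion survives if the doubtful patients had been classified the other way. Excluding them does not do that. At follow-up it also conditions on outcome: a patient who is no longer fatigued is a non-case without review, so any doubt arising in 3.2 concerns patients who still meet the fatigue and symptom criteria. Excluding them takes unrecovered, or not clearly recovered, patients out of the denominator after randomisation.

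The number of uncertain patients need not be equal between arms. The 3.1 screen uses HADS scores, which are a secondary endpoint, and sleep scores, when sleep is one of the symptom domains in objective b of the protocol. Treatment may therefore change who fails the screen. Evaluators also use hospital and GP records, and only the intervention arm has the programme's own clinical examination (Protocol 3.1, Intervention). What is at stake is how far the one stated robustness check on PIFS recovery can be relied on.

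**Working it through.** **Step 1. Who can be uncertain at follow-up.** Appendices 1 and 2 must both be met to be a case. The 3.1 screen is for those who would otherwise remain cases, and only those who fail it go to 3.2. A patient who no longer meets appendices 1 and 2 is a non-case whatever 3.2 would conclude. As written, uncertain patients at T1 or T2 therefore still meet the fatigue and symptom criteria.

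**Step 2. Notation.** The documents give no PIFS prevalence, recovery rate or count of uncertain patients, so there is no stated figure to reproduce. All inputs below are assumptions, and missing data are ignored. Per arm: N = T0 cases; R = patients no longer meeting appendices 1 and 2; U = uncertain patients; f = share of U that consensus settles as non-cases. Non-cases are taken to count as recovered, which the SAP does not say.

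- (a) all uncertain counted as cases: R/N
- (b) all uncertain counted as non-cases: (R + U)/N
- consensus result: (R + fU)/N
- exclusion: R/(N − U)

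Within an arm, exclusion always lies between (a) and (b). It is at least R/N, and it is at most (R + U)/N because that requires only U(N − R − U) ≥ 0. It therefore shows neither extreme.

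**Step 3. One arm, N = 100, R = 40, U = 10.** Exclusion gives 40/90 = 44.4%. The consensus result is (40 + 10f)/100.

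| f | consensus | exclusion | exclusion − consensus |
|---|---|---|---|
| 0 | 40.0% | 44.4% | +4.4 points |
| 0.5 | 45.0% | 44.4% | −0.6 points |
| 1 | 50.0% | 44.4% | −5.6 points |

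The break-even is f = R/(N − U) = 0.444. Over a wider assumed range (N = 100, R = 20 to 50, U = 5 to 20, f = 0 to 1), exclusion minus consensus runs from −15.0 points (R = 20, U = 20, f = 1: 25.0% against 40.0%) to +12.5 points (R = 50, U = 20, f = 0: 62.5% against 50.0%).

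**Step 4. Two arms, N = 100 and R = 40 in each, U = 15 (intervention) v 5 (control).**

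| analysis | intervention | control | difference |
|---|---|---|---|
| exclusion | 40/85 = 47.1% | 40/95 = 42.1% | +5.0 points |
| (a) uncertain = cases | 40% | 40% | 0 |
| (b) uncertain = non-cases | 55% | 45% | +10 points |
| consensus, f = 0.5 | 47.5% | 42.5% | +5.0 points |

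With the split reversed (5 v 15), every non-zero difference changes sign. With 10 v 10, all differences are zero.

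**Step 5. A true difference with equal uncertain counts.** With R = 40 v 25 and U = 10 in each arm, (a) and (b) both give 15.0 points, while exclusion gives 40/90 − 25/90 = 16.7 points. So although each arm's proportion stays between its bounds, the risk difference under exclusion can fall outside the values from (a) and (b).

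**The case against.** **A reader might infer that the analysis necessarily inflates recovery.** The documents do not support that. It is certain only against counting every uncertain patient as still a case. Consensus may settle some as non-cases, and if those count as recovered, exclusion can lower the figure (step 3). Nor is the +5.0 points peculiar to exclusion: at f = 0.5 the consensus analysis gives the same difference (step 4). The between-arm effect has no fixed sign, and the 15 v 5 split is illustrative.

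**The effect may vanish on another scale.** If the same fraction of the still-ill is uncertain in each arm, the odds ratio is unchanged. With 40 v 25 recovered and 20% of the still-ill excluded, (40/48)/(25/60) = 2.00 = (40/60)/(25/75). This stands if a logit link is used, which SAP section 4 does not specify, and only under proportional exclusion.

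**A reader might also take it as settled that uncertain patients can only be still-ill follow-up cases.** The footnote names no visit, and the only trial visit tied explicitly to this definition is T0. Exclusion at T0 selects on a pre-randomisation feature and is harmless in that respect. The follow-up reading rests on the recovery endpoint's reference to the appendix and on the separate 6-month and baseline criteria. It is well supported but not stated. The caseness algorithm is not visible in the text I have, so step 1 rests on the written rules alone.

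**If consensus settles every case, nobody is left uncertain** and the analysis excludes no one. That is a possible reading, and it shows that the term needs a definition.

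**Blinding and context.** Endpoint evaluation is blinded, which limits rater bias but does not equalise the number of uncertain patients. The SAP also plans per-protocol analyses with post-randomisation exclusions, so this footnote is not alone in that, and the full-analysis-set result stays intact.

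**Conclusion.** The point holds conditionally. If the footnote governs PIFS recovery at T1 or T2, as the SAP suggests, it removes randomised patients according to a post-randomisation outcome and does not test the alternative classification. It may raise or lower the recovery proportion and the treatment difference, depending on how consensus settles these patients and how many there are in each arm.

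The size cannot be derived from the documents. In the assumed example exclusion gives +5.0 points, where counting both ways gives 0 to +10. Those two values apply one rule to both arms; opposite rules would span −5 (40% v 45%) to +15 (55% v 40%).

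A systematic bias in favour of the intervention is not shown. Severity is minor: PIFS recovery is not the primary endpoint, which is SF-36 physical functioning at T1, and the analysis is supplementary.

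**What to change.** Replace the footnote's last sentence with text to this effect:

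- For recovery at T1 and T2, every T0 case stays in the analysis, in the arm as randomised.
- Two sensitivity analyses count patients of uncertain classification (a) as still PIFS cases and (b) as non-cases, each reported by arm with the treatment difference.
- Uncertain means that the two independent ratings differed before consensus.
- The SAP states whether a still-fatigued patient excluded under 3.2 counts as recovered.
- Exclusion is used only for uncertain classification at T0, in the subgroup analysis.

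The 6 months in the appendix heading should be reconciled with T0, T1 and T2 in the same edit. Defining uncertain by pre-consensus disagreement is one workable choice and requires the two ratings to be kept. The cost is SAP wording and one extra model run, with no new patient data. The downside is that a range is reported instead of one figure.

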### Algorithm for caseness assessment
